### **A. Summary of Protocol**

#### *a. Brief Description of Protocol (Study Design)*

This study will examine the effects of combining Varenicline (VRN) and *N*-acetylcysteine (NAC) on neural circuitry function and treating nicotine addiction. Healthy adult nicotine dependent cigarette smokers interested in quitting (n=150) will be randomized to one of four PBO-controlled conditions for 4 weeks: 1) VRN+NAC, 2) VRN+PBO, 3) NAC+PBO or 4) PBO+PBO. Following 1 week of medication, participants will be contingently reinforced for 3 days of smoking abstinence and be scanned using functional magnetic resonance imaging (fMRI) techniques, while nicotine deprived during a resting state and a cue-reactivity (CR) task. Participants will be followed over the next 3 weeks of treatment and clinical variables will be assessed.

#### *b. Specific Aims*

*Aim 1.* Identify the effects of *N*-acetylcysteine (NAC) + Varenicline (VRN) on resting neural network function and behavior. We will examine the individual and combined effects of VRN and NAC on neural circuitry function in humans. We will also identify relations between neural circuitry function and nicotine/smoking self-administration, withdrawal symptom severity and the maintenance of smoking abstinence over the duration of the study.

*Aim 2.* Examine the effects of NAC+VRN on drug-cue brain response and behavior. We will examine the individual and combined effects of VRN and NAC on cue-induced brain response and behavior in humans, focusing on limbic-striatal and corticostriatal networks. In these experiments we will also identify relations between neural circuitry function and nicotine/smoking self-administration and withdrawal symptom severity and the maintenance of smoking abstinence over the duration of the study.

[figure not shown]
*Exploratory Aim:* Participants will complete a Smoking Regulation Relapse task (SRRT) in the laboratory—the effects of VRN+NAC on smoking topography during the SRRT, and on subsequent smoking behavior and relapse will be examined. Whole brain fMRI analyses will be conducted, and relations between fMRI measures and clinical outcomes will be examined.

## B. BACKGROUND AND SIGNIFICANCE

Cigarette (henceforth nicotine) addiction is a chronic, relapsing brain disorder and remains the leading preventable cause of death and disability in the US [1], costing nearly \$200 billion each year [2]. Although ~20% of adults in the USA currently smoke [3], the majority want to quit. In spite of the breadth of research focused on improving health outcomes and reducing the societal burden caused by nicotine addiction, the majority of smokers who attempt to quit will relapse. Nicotine withdrawal-related disturbances in executive function, negative affect and reward processes compel a smoker to self-administer nicotine—each in turn representing the loss of control to remain abstinent and risk factors for relapse [4]. Thus, identifying the effects of nicotine addiction on mechanisms of self-regulation, and the value of novel medications for remediating dysregulated behavior are both needed in order to enhance interventions for treating nicotine addiction. Our preliminary data, along with the extant literature, suggest that the maintenance of nicotine addiction is subserved by dysregulated neural function in limbic-striatal and corticostriatal neural circuitry. While VRN may be effective in treating limbic-striatal circuitry that is associated with promoting abstinence and reducing acute withdrawal; NAC may be effective in treating corticostriatal circuitry function that is associated with relapse vulnerability. Thus, the current proposal seeks to investigate two medications (VRN & NAC), with potentially complementary effects on the two different brain circuits—limbic-striatal (VRN) and corticostriatal (NAC) circuitry—and that may therapeutically target two different phases in the recovery of nicotine addiction—the promotion of abstinence (VRN) and relapse prevention (NAC). The placebo (PBO)-controlled design in this proposal will allow the team to identify and translate between the neurobiological substrates and the neurocognitive underpinnings of the effects of VRN+NAC on smoking behavior in humans—thus, advancing our understanding of the pathophysiology of nicotine addiction.

The study will incorporate a Community Recruitment Vendor (CRV) campaign to assist in reaching out to the targeted study population. By identifying persons/businesses in the local area we will establish an agreement whereby for a monthly retainer, the CRV will promote the study using IRB approved recruitment materials within their unique network. The CRV will also be able to receive a bonus if a prospective participant identifies the CRV as their referral source and is successfully enrolled into the study protocol.

At the screening visit, informed consent, self-reported mood, smoking history, medical history, MINI International Neuropsychiatric Interview (MINI), and an MRI safety screening questionnaire will be administered by trained study staff and reviewed by approved study clinicians. Participants meeting all selection criteria will be scheduled for subsequent sessions

As with previous studies, we will make every effort to maximize participant retention via a thorough informed consent process, careful screening, and other practices (e.g., contacting participants with a reminder phone call the night before experimental sessions). A complete list of questionnaires and cognitive tasks that will be completed at each visit are included in Appendix 1.

The PI and research staff have all completed the University of Miami computer-based CITI Human Subjects Research Education Course. Male and female adult smokers, between 18 and 65years old, will be recruited, primarily through media advertisements (i.e. internet, print, radio). The inclusion/exclusion criteria are as follows:

### Entry Criteria

#### *Inclusion Criteria all subjects:*

1. Age 18 - 65
2. English fluency as demonstrated in providing informed consent and the ability to independently follow directions in completing assigned assessments and tasks
3. Functional vision (with corrective lenses as needed) to complete assigned assessments and tasks
4. Current nicotine dependent cigarette smoker with a minimum smoking history of two years
5. Interest in quitting smoking or contemplating a quit attempt in the next 6 months
6. If female, agreement to use birth control (any form of hormonal contraception such as Depo-Provera, daily oral contraception, transdermal patch, or Nuva-ring; intrauterine device; sterilization; or double barrier contraception, which is a combination of any two of the following methods: condoms, spermicide, diaphragm) to avoid pregnancy
7. Refrain from all other tobacco (i.e. dip/chew, cigars, cigarillos) and/or nicotine products (i.e. e-cigs, patches, gum/lozenges, inhalers/sprays) for the duration of study participation

#### *Exclusion Criteria all subjects:*

1. Past head injury or primary neurological disorder associated with MRI abnormalities, including dementia, MCI, brain tumors, epilepsy, Parkinson's disease, or demyelinating diseases
2. Any physical or intellectual disability affecting completion of assessments
3. Any contraindication to MRI
4. Positive urine drug screen for illicit substances (other than marijuana or cocaine).  
4a. For those testing positive for marijuana and/or cocaine, meet dependence criteria
5. Current or past psychosis
6. Electroconvulsive therapy in last 6 months
7. Use of antidepressants, medications with smoking cessation efficacy, or other psychotropic medications in the last month.
8. Positive urine pregnancy test or current breast-feeding status
9. Any other condition or concern that in the Investigator's opinion would impact participant safety, compliance with study instructions, or potentially confound the interpretation of the study results

As part of exclusion criteria #9, participants are specifically asked to not take part in any other research during their active participation in the protocol once eligibility at screening is made through the last visit day of the protocol.

Among females, pregnancy at screening will be exclusionary. Females of childbearing potential must agree to undergo additional pregnancy testing on Days 0 and 10 prior to the fMRI

**Genetic Evaluation Procedure.** After the subject gives informed consent, we will collect a venous blood sample of 15 ml. Blood samples obtained from this study will be collected at CNL and stored in the Translation Research on Addiction and Integrative Neuroscience (TRAIN) Laboratory directed by [name]. The blood samples will be analyzed at CNL and will be coded so that researchers analyzing DNA will have no way of identifying participants. We will use the DNA to examine if there are any relationships between brain functioning and genetic factors. There will be no identifiers except for a code number on the samples. A digital key to the code numbers will be maintained in password protected database on the MUSC network. The study PI ([name]) will have access to the password.

*Randomization & fMRI Session 1 (Day 0)*. During this session, participants will provide breath and urine samples to characterize current smoking behavior and BAC and fill out questionnaires to assess mood, cognitive state, and to characterize recent alcohol and nicotine use. Prior to receiving their study medication, both the participant and the research staff completing the visit will complete the Penetration of the blind (POB) assessment. POB completion by the participant and staff is done separately outside the presence of one another. At future visits when the POB is completed, research staff will complete their assessment at the conclusion of the visit without having viewed the participant's response.

Next, participants will be educated on guidelines for taking study medication and will be randomly assigned to one of four double-blind study medication arms: 1) NAC+VRN, 2) NAC+PBO, 3) VRN+PBO, or 4) PBO+PBO. Adverse events will be monitored throughout the study participation at every subsequent visit and participants will be encouraged to contact the study team in the interim if issues/concerns surrounding their medication and/or change in baseline health were to occur.

Participants will also be given instruction on their daily diary which logs the participant's smoking and related behaviors, as well as receive brief counseling on cessation strategies. They will also be given a take home resource material that may be helpful with their quit attempt.

While in the MRI scanner for their baseline session, fMRI-1, participants will lie still while undergoing a high resolution anatomical scan, as well as perform the CR task. Participants will be inside of the MRI scanner for approximately one hour. After the scanning portion of the visit, participants will perform the SRRT and smoke a cigarette through the CReSS smoking topography system.

**Cue Reactivity Task (CRT).** Participants will be scanned while performing a smoking CR task that involves viewing cigarette smoking-related images (e.g. cigarette) and non-smoking control images (e.g. pencil) over the course of ~8 ½ minutes [5, 7-13]. Participants will be asked to periodically report their level of craving in response to the images.

**Smoking Regulation Relapse analog task (SRRT: Fig. 2.** The SRRT was developed by the PI ([name]), and currently in use in his laboratory to assess relations between success in regulating mood and craving and subsequent smoking self-administration. The task is comprised of two phases. The first phase—similar to [6]—presents smoking or neutral images and instructs participants to either react to how the stimulus would make you feel Now (e.g. immediate satisfaction) or reframe the content into how it would make you feel Later (e.g. the deleterious health effects of smoking). Following each trial, self-reported craving ratings are collected. This is shown to be an effective probe of craving regulation that is mediated by corticostriatal function [6]. The task randomly presents 24 trials of neutral (n=12) and smoking (n=12) images, half of each divided into instruction with Now or Later, over a 6-min block. Participants have the choice to earn \$1 for each subsequent block up to 60 min., or quit the task and smoke a cigarette using a pocket CReSS system and topography measures recorded (e.g. # puffs, puff volume, IPI). In order to verify smoking topography measures, participants will be video recorded during while smoking through the CReSS device. Preliminary findings from a mood-regulation variant of the SRRT developed by

[figure not shown]

Figure 2: SRRT. Participants view control and smoking-related images and instructed to either react (Now) or regulate (Later) their response to the image and then rate their level of craving. Following the task, participants smoke their preferred brand of cigarettes using the CReSS system. Relations between self-report craving on the SRRT and smoking topography (e.g. # puffs, puff volume) will be examined.

the PI that is currently being used in a NIDA-funded study reveal that the magnitude of adaptive response in dACC during regulation is associated with less smoking self-administration ( $r^2 = .52$ ,  $p < .05$ ). Furthermore, NAC's strengthening of rsFC between the nucleus accumbens and dACC, as shown in Fig. 4, is associated with less smoking self-administration during the SRRT.

**Study Medication and Randomization.** This is a double-blind, placebo-controlled study of NAC and VRN. Participants will be randomly assigned to one of four double-blind experimental arms: 1) NAC+VRN, 2) NAC+PBO, 3) VRN+PBO, or 4) PBO+PBO. Participants will be instructed to begin tasking study medication the morning of Day 1. Medication response and tolerability/AEs will be assessed by study research staff, and revised by the clinical team as needed

- **N-Acetylcysteine (NAC).** NAC (or identical-appearing PBO) will be dosed at 1200 mg twice daily throughout the 28-day active treatment. The most common adverse effects of oral NAC are gastrointestinal discomfort (e.g. diarrhea, flatulence, nausea), but this medication is generally well-tolerated [18].
- **Varenicline (VRN).** VRN (or identical-appearing PBO) will be provided at the standard recommended dose (0.5 mg daily for 3 days, then 0.5 mg twice daily for 4 days, then 1 mg twice daily thereafter for the remainder of active treatment). The most common adverse effects of VRN are nausea, vivid dreams, and insomnia.
- **Medication Compounding, Packaging, Dispensing, and Adherence Monitoring.** The MUSC Investigational Drug Service (IDS) will be responsible for medication randomization, compounding, packaging, and dispensing. Pill counts and participant daily diaries will be used as additional medication adherence measures.

**Abstinence Period (Days 7-10).** Smoking abstinence from the target quit date (Day 7) until Day 10 will be confirmed via breath CO samples (abstinence <6 ppm). Participant diaries and medication packs will be reviewed for safety and compliance. Brief assessments on craving, mood and withdrawal symptoms will also be completed.

**fMRI -2 Experimental Visit (Day 10).** Participants will be contacted two days prior to the scheduled fMRI session and reminded of session-specific details. Participants will fill out questionnaires regarding mood, withdrawal symptoms, and caffeine, nicotine, and food intake over the last 24 hours. Expired CO and BAC will be collected to confirm compliance. While in the MRI scanner, participants will lie still while undergoing a high resolution anatomical scan, as well as perform the CR task. Participants will be inside of the MRI scanner for approximately one hour. After the scanning portion of the visit, the participant will complete the POB assessment followed by the participant performing the SRRT and smoking a cigarette through the CReSS smoking topography system. Participants will again be video recorded while smoking through the CReSS device for visual confirmation of the device data collection.

**Follow-Up Assessments (Days 11-35).** After the fMRI session, participants will continue to take study medication for another 18 days (Days 11-28). They will return to the clinic on Days 14, 21, 28, and 35 to submit expired CO and urine samples to determine smoking status and medication compliance, as well as complete mood, nicotine craving/withdrawal, and safety assessments. Participants will return to the clinic on Day 35 for a one-week post medication safety, smoking assessment, and POB.

At the discretion of the PI's additional urine drug screens, pregnancy, and cotinine tests can be added to a visit day in order to address any unexpected safety and or data integrity concerns within a participant's active participation within the protocol. As needed when urine cotinine collection is not feasible, saliva specimens will be collected for cotinine assay.

[figure not shown]
**Duration.** Participation in the study will take about 6 weeks with a total of 10 visits lasting approximately 13-14 hours in total. The first visit (screening/training) will last up to 4 hours; each of the 7 clinic visits (Days 7-9, 14-35) will last about 15 minutes each, and the fMRI Experimental visits (Day 0 and 10) will each last approximately 4 hrs.

**Participant Compensation.** Participants will be compensated up to \$500 for completion of all study procedures. Participants will receive \$60 for the screening visit (\$20 for successful completion of the blood draw, online surveys, and MINI Plus clinical interview, and \$40 for completing the training portion of the visit), \$110 for the baseline fMRI-1 (Day 0) and experimental fMRI-2 sessions (which includes \$1 for every 6 minutes during SRRT up to 60 minutes total), \$60 for achieving biochemically-confirmed abstinence from smoking for 3 days (\$20/day), \$30 for each additional clinic visit (Days 14-35) to assess smoking status and complete assessments, and an additional \$40 bonus for completing all study procedures. Compensation will be made for each session completed and will not be contingent upon completion of the entire study. During the informed consent procedure, participants will be notified that they can withdraw from the study at any time under no penalty.

Additionally, due to the structured nature of the protocol's visit schedule, when a participant is unable to meet a scheduled visit (Days 7-10) due to an unforeseen conflict (i.e. transportation issue), study personnel will explore alternatives (i.e. provide for taxi service) to allow for the visit schedule to continue as planned.

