Brain-behavior data analysis plan: First, POMS, SJW and mCEQ subscale scores will be computed, and motivation to smoke and days to first cigarette (lapse) following the experimental visit will be recorded for each subject. Next, to examine the interactive effects of treatment on self-report and rsFC, each scale will be entered as a regressor of interest in separate between subjects ANOVA's in the Conn Toolbox.

Smoking topography analysis plan: Craving regulation performance will be assessed by calculating change scores (Later-Now) from craving ratings. T-tests will be performed to analyze correlations between craving ratings, smoking topography variables: time to 1st puff (i.e. task blocks); puff volume (milliliters) and number of puffs. Regression analyses will explore relations between SSRT performance and strength of rsFC between ROI's in Figure 11.

Real-world smoking behavior analysis: Number of days to lapse (DTL) following the lab visit on day 10 will be recorded. Regression analyses entering DTL on brain cue-reactivity and rsFC will be performed and relations explored.

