#### b. **Specific Aims**

*Aim 1.* Identify the effects of *N*-acetylcysteine (NAC) + Varenicline (VRN) on resting neural network function and behavior. We will examine the individual and combined effects of VRN and NAC on neural circuitry function in humans. We will also identify relations between neural circuitry function and nicotine/smoking self-administration, withdrawal symptom severity and the maintenance of smoking abstinence over the duration of the study.

*Aim 2.* Examine the effects of NAC+VRN on drug-cue brain response and behavior. We will examine the individual and combined effects of VRN and NAC on cue-induced brain response and behavior in humans, focusing on limbic-striatal and corticostriatal networks. In these experiments we will also identify relations between neural circuitry function and nicotine/smoking self-administration and withdrawal symptom severity and the maintenance of smoking abstinence over the duration of the study.

*Exploratory Aim:* Participants will complete a Smoking Regulation Relapse task (SRRT) in the laboratory—the effects of VRN+NAC on smoking topography during the SRRT, and on subsequent smoking behavior and relapse will be examined. Whole brain fMRI analyses will be conducted, and relations between fMRI measures and clinical outcomes will be examined.

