*Exploratory Clinical Outcomes.* The clinical outcomes assessed in this study are designed to assess relapse for 3 weeks following a period of monitored abstinence under PBO-controlled medication conditions. Although the study is not specifically powered to detect the secondary hypothesis of an additive effect of VAR and NAC on abstinence from nicotine (2x2 interaction), the stated sample size will allow for the estimation of effect sizes and the precision of the variance in order to inform a subsequent larger study. Based upon completion rates in our prior studies, we anticipate a 15% attrition rate between randomization and the end of the clinical portion of the study; thus, we anticipate that 94 of the 150 randomized participants will provide secondary clinical data for analysis (23 in each treatment assignment). Assuming that no additive effect is present and that the NAC/PBO abstinence rate is 10%, we will have 80% power with a type 1 error rate of 5% to detect an abstinence rate of 33% in the VRN group.

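### A study cigarette is scheduled at the end of Day 10, just before the lapse clock starts, so follow-up describes smoking after a laboratory cigarette, not maintained abstinence from the quit date

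*Combined protocol and SAP*

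**What the plan says.** In the protocol part, section C sets the quit date at Day 7 and confirms abstinence to Day 10 by breath CO below 6 ppm. Participant Compensation pays 20 dollars a day for those three days. On Day 10 the scan comes first, then the blinding questionnaire "followed by the participant performing the SRRT and smoking a cigarette through the CReSS smoking topography system". The same paragraph has the smoking video-recorded. The caption to Figure 2 is equally unconditional: "Following the task, participants smoke their preferred brand of cigarettes using the CReSS system". The description of the task itself reads differently: "Participants have the choice to earn \$1 for each subsequent block up to 60 min., or quit the task and smoke a cigarette".

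Three places describe what follow-up is for:

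- Specific Aims (sections A.b and 1.b): Aims 1 and 2 both promise to relate brain measures to "the maintenance of smoking abstinence over the duration of the study".
- Section 1.d, Exploratory Clinical Outcomes: these outcomes are "designed to assess relapse for 3 weeks following a period of monitored abstinence under PBO-controlled medication conditions". Planning abstinence rates of 10% and 33% are given, without a definition of abstinence.
- Data Analysis, real-world smoking behavior: "Number of days to lapse (DTL) following the lab visit on day 10 will be recorded". The brain-behavior paragraph also takes lapse as the first cigarette after the experimental visit.

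**The concern.** The monitored abstinence is ended by a study procedure before the follow-up clock starts. A participant who does what the Day 10 paragraph describes has smoked three days after the quit date, on medication and under supervision. Days to lapse is then the time to the next cigarette after a supplied one.

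Two things make this more than loose wording. First, Background and Significance assigns promotion of abstinence to VRN and relapse prevention to NAC, so what state follow-up starts from bears on the trial's own rationale. Second, exposure to the study cigarette is measured after randomisation and may depend on arm. Time to first puff, puff count and puff volume are study outcomes, and the exploratory aim examines drug effects on them. The text after Figure 2 also links the connectivity effect of NAC to less smoking during the same task. Participants could thus enter follow-up with different exposures by arm, and the plan does not say how this would be shown or interpreted.

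**Working it through.** **1. Order of events (section C).**

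| Time | Event |
|---|---|
| Day 7 | Quit date |
| Day 7 to arrival on Day 10 | CO-confirmed, paid abstinence |
| Day 10 | Scan, then blinding questionnaire, then task and cigarette |
| After the Day 10 visit | Days-to-lapse clock starts |
| Days 14, 21, 28, 35 | CO and urine for smoking status |

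Only the CO checks up to arrival on Day 10 measure abstinence after the quit date and before the study cigarette. The Data Analysis section plans no comparison of them by arm.

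**2. Who smokes.** The Day 10 paragraph and the Figure 2 caption have participants smoke. The task description offers a choice, with money for 6-minute blocks up to 60 minutes (60 / 6 = 10 blocks), and does not say whether someone who lasts 60 minutes still smokes. The share who smoke is therefore unsettled, up to all who complete Day 10.

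**3. What each quantity becomes.**

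- Continuous abstinence from Day 7: impossible for anyone who smokes the study cigarette.
- Days to lapse: time from the visit to the next cigarette. It is well defined if the supervised cigarette is left out.
- Abstinence on Days 14 to 35: measurable, but conditional on what happened on Day 10. Section 1.d does not say from when it is counted.

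**4. The plan's power figure.** Inputs from section 1.d: 10% and 33%, alpha 5% (sidedness not stated), 94 participants with clinical data, taken as stated. On the VRN margin that is 94 / 2 = 47 per group.

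Power = Φ[(d − 1.96 × SE0) / SE1], with

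- d = 0.33 − 0.10 = 0.23
- SE0 = √(2 × 0.215 × 0.785 / 47) = 0.0848
- SE1 = √((0.10 × 0.90 + 0.33 × 0.67) / 47) = 0.0814

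Result: (0.23 − 0.1661) / 0.0814 = 0.785, and Φ(0.785) = 0.784. With the unpooled error it is Φ(0.23 / 0.0814 − 1.96) = 0.807. The stated 80% therefore reproduces, two-sided, for VRN against no VRN. This neither supports nor weakens the point, which concerns what is being estimated.

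**5. Illustration only.** Suppose the 10% and 33% were set without the Day 10 cigarette in mind, and that a share f of would-be abstainers stays abstinent after it, equally in both groups. The documents give no value for f. Using the first formula at 47 per group:

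| f | Rates | Power |
|---|---|---|
| 1.0 | 10% / 33% | 0.784 |
| 0.9 | 9% / 29.7% | 0.726 |
| 0.8 | 8% / 26.4% | 0.661 |
| 0.7 | 7% / 23.1% | 0.590 |
| 0.6 | 6% / 19.8% | 0.515 |
| 0.5 | 5% / 16.5% | 0.435 |

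**The case against.** The best defence is that the analysis text already starts lapse after the visit, so the supervised cigarette is implicitly set aside. For days to lapse that is right, and only an explicit sentence is missing. It does not extend to the abstinence outcome in section 1.d, which has no stated origin, or to the wording of the aims.

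The design is also declared. The task is named a relapse analog, and the overview and exploratory aim plan to relate it to later smoking. Using such a task before follow-up is a legitimate choice. What is missing is a description of the follow-up outcome that reflects it.

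The consequences are bounded. The primary aim is fMRI signal, the Day 10 scan precedes the cigarette, and the clinical outcomes are labelled exploratory.

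A reader might infer three stronger things that the documents do not support:

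- That every participant smokes on Day 10. The choice wording in the task description leaves this open.
- That abstinence and relapse cannot be measured at all. CO and urine on Days 14 to 35 still show abstinence after the visit, and the procedure is common to all arms, so the randomised comparison holds.
- That abstinence must be 0% in every arm, contradicting the planned 10% and 33%. That follows only if all smoke, the cigarette counts, and those rates mean continuous abstinence from Day 7. Section 1.d never defines them so.

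**Conclusion.** The point stands for the estimand. Participants who follow the Day 10 paragraph cannot deliver maintained abstinence over the study, and the three-week follow-up measures lapse or abstinence after a supervised laboratory cigarette. Comparisons of post-visit outcomes by arm are valid for that question. Their extension to relapse prevention starting from unbroken abstinence is not supported by the design.

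No numerical bias is shown. The power figure is reproducible, and the losses in the illustration depend wholly on the assumed f. Treatment comparisons on the Day 10 scan are unaffected. The parts of Aims 1 and 2 that relate scan measures to later abstinence take on the narrower meaning. The conclusion assumes that the Day 10 paragraph and the Figure 2 caption describe what is done. If some participants decline to smoke, follow-up starts from a mixture of states that may differ by arm. This is worth correcting before analysis, but it does not threaten the primary aim.

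**What to change.** 1. In the Specific Aims (A.b and 1.b) and in section 1.d, restate the clinical quantity as lapse or abstinence after the Day 10 laboratory cigarette. State that the supervised cigarette does not count, and apply the post-visit origin already used for days to lapse to the section 1.d abstinence outcome.
2. Add a supplementary VRN x NAC analysis of CO-confirmed abstinence from Day 7 to arrival on Day 10. It bears on the promotion-of-abstinence question. Label it as incentivised. It should not replace the follow-up outcome, because the window is three days long, payment may compress differences between arms, and it says nothing about relapse.
3. Report Day 10 smoking by arm beside days to lapse: whether smoked, puff count and puff volume. Keep this descriptive, since these are post-randomisation measures.
4. Reconcile the task description, where smoking is a choice, with the Day 10 paragraph and the Figure 2 caption, where participants smoke.

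The cost is wording, one extra analysis and a descriptive table, all from data the protocol already collects. The price is a narrower clinical claim for the follow-up period.
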